Primary Objectives: Assess the relative effectiveness of the ABC intervention combined with Head Start (HS)-level asthma education (ABC group) in improving asthma morbidity compared to HS-level asthma education alone (Control group) in preschool children with symptomatic asthma. Primary Hypothesis (#1): Participants receiving the ABC intervention will have more symptom free days at the 6-, 9-, and 12-month evaluations when compared with participants in the control group. (#2): Participants receiving the ABC intervention will have reduced morbidity, including decreased urgent care utilization (hospitalizations/ED visits measured by caregiver report as well as insurance payer data), improved quality of life, improved asthma control, and fewer courses of oral steroids, when compared with participants in the Control group at the 6-, 9-, and 12-month evaluations.

Secondary Objectives: Assess the degree to which HS program-level adoption, implementation and maintenance of asthma education activities (stratified as high implementation vs. low implementation) moderates the impact of child-level treatment assignment (ABC vs. Control) on measures of asthma morbidity, including symptom-free days, urgent care, quality of life, asthma control and oral steroids.

Secondary Hypothesis (#3): Participants receiving the ABC home-based intervention combined with high implementation of HS-level asthma education will have reduced asthma morbidity, including decreased urgent care utilization, improved quality of life, improved asthma control, and fewer courses of oral steroids, when compared with participants receiving the ABC intervention in low implementation of HS-level asthma education, or Control group participants at the 6-, 9-, and 12month evaluations. The secondary outcome measures include other measures of asthma morbidity (i.e., ED visits and hospitalizations, oral steroid bursts, asthma control and caregiver quality of life).

3. Background (briefly describe pre-clinical and clinical data, current experience with procedures, drug or device, and any other relevant information to justify the research)

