Previous efficacy studies have suggested that asthma education programs can be effective in improving overall management of asthma for preschool children. Multiple studies have demonstrated that home asthma educational interventions can increase the number of symptom free days, decrease frequency and severity of asthma flares, decrease ED visits and hospitalizations, and improve quality of life. Asthma education interventions have been shown to reduce asthma morbidity across diverse populations, including in preschool age and low-income minority children. Schoolbased asthma programs are a promising strategy for asthma education because of the potential to reach large numbers of children and directly teach them asthma self-management skills. School programs offer the further advantage of being able to deliver asthma education to low-income children who may not be seen for regular asthma medical care. Most of these programs, however, have been conducted in elementary schools and focused on the child's efforts to self-manage and are of limited application in a pre-school age population. In a prior study we found that our **Asthma Basic Care (ABC)** intervention led to significant short-term improvements in symptom free days, along with a greater rate of reduction in courses of oral steroids over 18 months, relative to usual care in low-income, minority children. However, for these promising asthma intervention strategies

Date: January 26, 2017

Principal Investigator: [name].

Application Number: NA_00046455

to have sustainable public health impact for low-income, minority children, they must be integrated within those medical, educational and social structures that serve these high risk children. We therefore propose to draw on our established health and research partnership with Head Start programs in Baltimore City to test the feasibility of implementing the ABC home-based asthma education intervention with demonstrated efficacy into a Head Start venue.

4. Study Procedures

- a. Study design, including the sequence and timing of study procedures (distinguish research procedures from those that are part of routine care).

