In order to enhance the efficacy, reach, integration and sustainability of the proposed home-based asthma education intervention, we will train and facilitate Head Start staff to implement and deliver the HS-level asthma education program, utilizing existing community resources whenever possible. The HS-level asthma education program will consist of the following four components: 1) bi-annual Staff Training Workshops (for which HS staff will receive continuing education credit), 2) provision of relevant asthma educational materials drawn from public resources, 3) identification and facilitation of community resources relevant for achieving goals, and 4) ongoing expert facilitation of Head Start initiated asthma education activities (e.g. parent workshops, health fairs, newsletters)

- a. Study duration and number of study visits required of research participants. The study duration is 12 months for each participant. All participants will complete 5 surveys. The intervention condition will also receive 3 home visits and 4 phone calls. Head Start staff will be offered the opportunity to attend asthma education workshops which contain 8 modules and a postevaluation two times a year.
- b. Blinding, including justification for blinding or not blinding the trial, if applicable. N/A
- c. Justification of why participants will not receive routine care or will have current therapy stopped.

All subjects will receive an asthma educational program within the Head Start setting which is not currently provided. Participants in the intervention condition will receive additional intervention.

- d. Justification for inclusion of a placebo or non-treatment group.
Both groups will receive a Head Start level educational intervention, thus there is no nontreatment group. The intervention group will receive additional intervention sessions.
- e. Definition of treatment failure or participant removal criteria.
Any participant can leave the study at any time. Participants will be removed from the study prior to randomization if the baseline assessment is not complete. Treatment failure is defined as subjects not completing the home visits. After the participant is randomized, subjects will not be removed from the study by investigators.
- f. Description of what happens to participants receiving therapy when study ends or if a participant's participation in the study ends prematurely.

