This study does not provide experimental medical care for the participants but does encourage the families to keep all appointments with the child's PCP. The child's medical care will not be affected if the family ends their participation in the study prematurely. There are no known risks of exiting the study prematurely.

5. Inclusion/Exclusion Criteria

Inclusion:

- Age 2-6 years
- Currently enrolled in Baltimore City HS program
- Physician diagnosis of asthma or reactive airway disease (RAD)

Date: January 26, 2017

Principal Investigator: [name].

Application Number: NA_00046455

Exclusion:

- Current participation in another respiratory research study
- Families unwilling or unable to participate
- A sibling enrolled in the study
- Non-English speaking
- Plans to move out of the Baltimore area in the next year Living in transitional housing

6. Drugs/ Substances/ Devices N/A

- a. The rationale for choosing the drug and dose or for choosing the device to be used.
- b. Justification and safety information if FDA approved drugs will be administered for non-FDA approved indications or if doses or routes of administration or participant populations are changed.

Study Statistics

- a. Primary outcome variable.

The primary outcome is symptom free days which is a well-recognized, accepted index of asthma morbidity often used to assess the effectiveness of new therapies in children. A measure of SFD is calculated by subtracting the numbers of days and/or nights with asthma symptoms (i.e., cough, wheeze, shortness of breath) in the past month from 30 days. Studies utilizing clinical and education interventions have demonstrated that improvements of 2-3 SFD /month are feasible and clinically meaningful.

- b. Secondary outcome variables.

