Secondary outcomes include caregiver-reported healthcare utilization for urgent (ED visits and hospitalizations) and non-urgent (primary and specialist care) asthma visits, caregiver-reported oral steroid bursts, caregiver-reported asthma control and caregiver quality of life. We will also collect objective data on healthcare utilization from insurance payers to validate caregiver report. In addition, at the HS level, we will assess overall HS participation in the HS-level asthma education program and any additional programs or institutional changes that would indicate adoption, implementation and maintenance of asthma education as a core HS health goal and changes in HS staff knowledge, attitudes and practices related to asthma management.

- c. Statistical plan including sample size justification and interim data analysis.

The power analysis is based on differences in symptom free days between the ABC group and the control group. We expect to recruit 406 total families (203 each group) and anticipate up to 15% of those enrolled will be lost to follow-up for a final sample of 346 families included in the analyses. We chose this sample size because under a variety of scenarios, discussed below, it is considered sufficient to detect a similar increase in symptom free days seen in our previous study. Symptom free days will be assessed at baseline, 3-, 6-, 9- and 12-months postrandomization. Choices for treatment effects, variability, associations (to account for the longitudinal nature of the study), and loss to follow up rates were informed by our previous

Date: January 26, 2017

Principal Investigator: [name].

Application Number: NA_00046455

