study, as well as from the literature. The power calculations were obtained using the software package SAS version 9.2 (SAS Institute, Cary NC). We expect that both groups will have a mean (SD) number of symptom free days 23.65 (6.85) in a month at baseline. In our previous study, the ABC group experienced a 23% increase in symptom free days over the no-contact control group at 6 months post-randomization. This application proposes to achieve a similar, if not higher, increase in symptom free days at 6 months. Table 1 gives a summary of the estimated total sample size that we will need to detect effect under different power assumptions (power = 0.8, 0.9) and within-subject association (parameterized as a latent effect inducing correlations of ($\rho = 0.5, 0.6, \text{ or } 0.7$). Inspection of the table below reveals that we will have 90% power to detect an approximate 23% increase in symptom free days for the ABC group at 6 months post-randomization.

Table 1

Power = 0.8		Power = 0.9	
ρ	Estimated Total N	ρ	Estimated Total N
0.5	188	0.5	248
0.6	236	0.6	316
0.7	268	0.7	346

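### Sample size and power rest on ABC's gain over a no-contact control, but the trial tests ABC against active Head Start education; restate the power in days for that contrast

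*Combined protocol and SAP*

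**What the plan says.** Study Statistics, item c, chooses the sample size because "it is considered sufficient to detect a similar increase in symptom free days seen in our previous study". It describes that earlier result as follows: "the ABC group experienced a 23% increase in symptom free days over the no-contact control group at 6 months post-randomization". It then adds: "This application proposes to achieve a similar, if not higher, increase in symptom free days at 6 months". Table 1 and the 90% power statement follow from this 23%. The Background (section 3) reports ABC's earlier results "relative to usual care in low-income, minority children", apparently from the same study.

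The comparator here is different. The primary objective (section 2) evaluates ABC plus HS education "compared to HS-level asthma education alone (Control group) in preschool children with symptomatic asthma". Section 4, on the justification for a placebo or non-treatment group, states: "Both groups will receive a Head Start level educational intervention, thus there is no nontreatment group". The item before it adds: "All subjects will receive an asthma educational program within the Head Start setting which is not currently provided".

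Study Statistics, item a, defines symptom free days (SFD) as 30 minus the symptomatic days in the past month, and says that "improvements of 2-3 SFD /month are feasible and clinically meaningful".

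**The concern.** The planning effect belongs to one contrast (ABC versus no contact) and the trial runs another (ABC plus HS education versus HS education). Because HS education is given in both arms, the trial estimates only what ABC adds to it. Any benefit that HS education brings to controls tends to shrink that increment, unless the two programs reinforce each other. The plan applies no discount for the change of comparator and gives no estimate for the new one.

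What is at stake is the meaning of the 90% figure. If the effect behind it cannot plausibly occur in this contrast, readers do not know what the trial can detect. The plan also never gives its power for the difference that it calls clinically meaningful.

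**Working it through.** **Inputs.** From Study Statistics, items a and c: expected mean 23.65 and SD 6.85 SFD per month; scale maximum 30; planning effect 23%; 203 per arm enrolled, 346 analysed (173 per arm) after 15% loss; within-subject correlation 0.5, 0.6 or 0.7; meaningful difference 2-3 days. Alpha and sidedness are not stated, so I assume two-sided 0.05. I also assume that the 6-month SD equals 6.85, and I take the 23% relative to 23.65, because its base is not given.

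**1. The plan's own figure.** 0.23 × 23.65 = 5.44 days. The two-mean formula for 90% power gives n per arm = 2 × (1.960 + 1.282)² × 6.85² / 5.44² ≈ 33.3, so 34 per arm, or 68 in total. Table 1 gives 346 at correlation 0.7. Repeated-measures averages, change scores, baseline adjustment, inflated variances and a two-proportion version give 34 to 254 for that cell. Table 1 therefore does not reproduce from the stated inputs, and the difference actually used is unknown. That is a separate problem, but it limits what can be concluded below. The dropout step is consistent: 406 × 0.85 = 345.1.

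**2. What 23% requires.**
- With controls at 23.65, the ABC mean is 23.65 + 5.44 = 29.09 out of 30.
- A perfect score of 30 would be a gain of 30/23.65 − 1 = 26.8%, so there is little room for anything higher.
- A 23% gain is impossible once the control mean exceeds 30/1.23 = 24.39, that is, once controls improve by more than 24.39 − 23.65 = 0.74 days.
- If controls gained 2 days, the largest possible difference would be 30 − 25.65 = 4.35 days, or 17%.

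**3. What 346 can detect.** SE = 6.85 × √(2/173) = 0.737. Power = Φ(d/SE − 1.96). With baseline adjustment, SE is multiplied by √(1 − ρ²), taking ρ as the correlation between baseline and 6 months.

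| Difference (days) | % of 23.65 | Unadjusted power |
|---|---|---|
| 2.0 | 8.5 | 77.5% |
| 2.5 | 10.6 | 92.4% |
| 3.0 | 12.7 | 98.3% |

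For 2 days with baseline adjustment, power is 88.0% (ρ = 0.5), 92.4% (ρ = 0.6) or 96.7% (ρ = 0.7). Unadjusted, 90% power corresponds to (1.960 + 1.282) × 0.737 ≈ 2.39 days, which is 44% of 5.44 and inside the plan's meaningful range.

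**4. Table 1 at face value.** Suppose instead that 346 does give exactly 90% for the full 23% at ρ = 0.7. If a fraction f of the effect remains, power = Φ(f × 3.242 − 1.96): 68% at f = 0.75 and 37% at f = 0.5. On the mean and SD, the same fractions (4.08 and 2.72 days) give more than 99% and 96%. The two readings are far apart, and the plan does not let a reader choose between them.

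**The case against.** The strongest reply is that the two programs may reinforce each other. Section 4, under the HS-level asthma education program, says that the program is delivered partly to make the home intervention more effective, so a reason for expecting a comparable effect does exist. This stands as a rationale, and it means that a smaller increment is plausible but not established. It carries no figure, however, and the 30-day ceiling leaves it little room.

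Three further points are fair. The plan says its effect assumptions drew on the literature as well as on the previous study. The base of the 23% is unstated, so 5.4 days is one reading of it. The 2-3 days comes from unspecified clinical and education interventions with no comparator named; it can serve as a meaningful difference but is not evidence of the add-on effect.

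A reader might also infer more than the documents support:
- **That the plan misstates its question.** It does not. The opening summary, section 2 and the study design text in section 4 all describe ABC plus HS education against HS education alone.
- **That Hypothesis #3 predicts benefit to controls.** It predicts moderation of ABC's effect by HS implementation and does not split controls by implementation.
- **That giving spacers at baseline dilutes the effect.** They go to any family without one, before randomization, in both arms. Nothing shows what the previous study did.
- **That a gain of 2-3 days would count as failure.** The 23% is a planning value. Hypothesis #1 asks only for more SFD in the ABC group.

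**Conclusion.** The mismatch is explicit in the text: sample size and 90% power are justified by a gain over no contact, while both arms here receive a newly introduced education program. Taken relative to 23.65, the 23% could be reached only if controls improved by no more than about 0.74 days, so the stated power is tied to an effect that this contrast can hardly show.

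It is tempting to conclude that the trial is underpowered. The documents do not support that. On the stated mean and SD, 346 analysed children give 90% power for about 2.4 days, so more than half of the 5.4 days could be lost before power fell below 90%. The low figures obtained from Table 1 at face value depend on a table that cannot be reproduced. What can be said is that 90% power does not hold at the 2-day end of the plan's own range without baseline adjustment, nor with adjustment at a correlation of 0.5 (88%).

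These figures rest on a 6-month SD of 6.85, two-sided alpha 0.05, 173 analysed per arm and a comparison at 6 months.

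**What to change.** In Study Statistics, item c:

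1. Remove the statement that the increase will match or exceed the earlier one, and stop using the no-contact result as the planning target. It can remain as background, labelled with its comparator.
2. State the detectable difference for ABC + HS versus HS alone in days. Use the 2-3 days of item a as the clinically meaningful difference, and say that it is not a demonstrated add-on effect.
3. State alpha, sidedness and the analysis model, and give the power at 346 analysed. Under the assumptions above: about 78%, 92% and 98% unadjusted for 2, 2.5 and 3 days, and 88-97% for 2 days with baseline adjustment at correlation 0.5-0.7. If the sponsor's model or SD differs, substitute its own figures.

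This costs only protocol wording. Enrolment stays at 406. The downside is a less favourable stated power at 2 days.

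### The stated 90% power for an approximate 23% increase in symptom-free days does not follow from the plan's own mean and SD (23.65, 6.85); effect, SD, alpha, model and N need to be reconciled, with N=406 unchanged

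*Combined protocol and SAP*

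**What the plan says.** All of this is in Study Statistics, item c, of the combined protocol and SAP unless noted.

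- **Mean and SD.** "We expect that both groups will have a mean (SD) number of symptom free days 23.65 (6.85) in a month at baseline". No 6-month mean or SD is given.
- **Effect.** It comes from the earlier study, where "the ABC group experienced a 23% increase in symptom free days over the no-contact control group at 6 months post-randomization". For this trial, "This application proposes to achieve a similar, if not higher, increase in symptom free days at 6 months". It is never expressed in days.
- **Correlation.** Table 1 varies the "within-subject association (parameterized as a latent effect inducing correlations of" 0.5, 0.6 or 0.7. The variance of that latent effect is not given.
- **Table 1, total N at 80% / 90% power.** 188/248 at rho 0.5, 236/316 at rho 0.6 and 268/346 at rho 0.7.
- **Conclusion.** "Inspection of the table below reveals that we will have 90% power to detect an approximate 23% increase in symptom free days". The claim concerns the ABC arm at the 6-month visit.
- **Analysed sample.** The plan recruits 406 families and will "anticipate up to 15% of those enrolled will be lost to follow-up for a final sample of 346 families included in the analyses". The figure 346 is the 90% cell at rho 0.7.
- **Source of inputs.** "Choices for treatment effects, variability, associations (to account for the longitudinal nature of the study), and loss to follow up rates were informed" by the earlier study and the literature. Alpha, sidedness and the power model are not stated.

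Study Statistics, item a, bounds the outcome at 30 days. It regards gains of two to three days a month as attainable and worthwhile.

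**The concern.** This is the trial's only sample-size justification, and it concerns the primary outcome at the primary time point. A reader who applies 23% to the stated mean and SD gets a sample several times smaller than any entry in Table 1, so the sentence and the table do not appear to describe the same effect.

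The stake is how the result will be read, not whether the trial is large enough. If the plan is taken at its word, the design target is about 5.4 days, and a true difference of two to three days could be dismissed as below what the trial was built to find. The plan gives no power for a difference of that size.

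**Working it through.** **Inputs.** From the plan: mean 23.65, SD 6.85, effect 23%, power 80% and 90%, equal allocation, 346 analysed, outcome 0 to 30. Assumed because not stated: two-sided 5%, and 6-month control mean and SD equal to baseline unless varied below.

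**1. The plan's figure from its own inputs.** Difference = 0.23 × 23.65 = 5.44 days, and 5.44/6.85 = 0.79 SD. With total N = 4(z₁₋α/₂ + z₁₋β)² SD²/δ²:

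- 90% power: 4 × 10.507 × 46.92/29.59 ≈ 67; an exact t-test gives 69
- 80% power: 4 × 7.849 × 46.92/29.59 ≈ 50; an exact t-test gives 52
- 90% power at two-sided 1%: 98 (exact t-test)

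Table 1 has 248 to 346 and 188 to 268. The stated N is not reproduced.

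**2. Does the longitudinal model explain it?** N for 5.44 days at 90% power, total SD 6.85, rho 0.5/0.6/0.7:

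| Model | N |
|---|---|
| Baseline-adjusted | 52/45/37 |
| Change score | 69/56/43 |
| Mean of four visits | 44/49/54 |
| Table 1 | 248/316/346 |

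None exceeds about 69. In the first two, N falls as rho rises, whereas Table 1's N rises.

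**3. Does a different control mean explain it?** Exact t-test at SD 6.85 and 90% power, with 23% applied to the control mean: 15 days needs 168, 18 days needs 118, 20 days needs 96. For 346, the detectable difference is 6.85 × √(4 × 10.507/346) = 2.39 days, so the control mean would be 2.39/0.23 ≈ 10.4 days.

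**4. Does a larger SD explain it?** In a single-visit comparison, needing 346 for 5.44 days takes an SD of about 15.6. The largest SD possible on a 0 to 30 scale with mean 23.65 is √(23.65 × 6.35) = 12.25. If latent variance is added on top of 6.85, the single-visit SD becomes 6.85/√(1−rho) = 9.7/10.8/12.5. A change-type comparison, which doubles that variance, then gives about 269/336/447 at 23%. At 23.6% it gives 192/256, 239/319 and 318/424 (80%/90%), close to the first two rows of Table 1 but not to the rho 0.7 row (268/346) that supplies 346.

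**5. Does a bounded-outcome model explain it?** Overdispersed binomial: variance = 30p(1−p)(1 + 29 rho), with p the mean divided by 30, and N = 2(z₁₋α/₂ + z₁₋β)²(V₁ + V₂)/δ².

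- Control mean 18, 23% increase (δ = 4.14). At rho 0.5, V₁ = 111.6 and V₂ = 89.9, so N = 2 × 10.507 × 201.5/17.14 ≈ 247. All rows (80%/90%): 185/247, 219/293 and 254/340, within about 7% of all six cells. The SDs are about 10 to 12.
- Control mean 23.65: V₁ + V₂ = 91.3 at rho 0.5, so N = 2 × 10.507 × 91.3/29.59 ≈ 65. At rho 0.7 it is 89.

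**6. What 346 can detect at SD 6.85.** Unadjusted: 90% power at about 2.39 days (2.39/23.65 = 10.1%). Power is 77% at 2 days, 92% at 2.5 and 98% at 3. With baseline adjustment the 90% figure is 2.39 × √(1−rho²) = 2.07/1.91/1.70 days at rho 0.5/0.6/0.7.

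**The case against.** The strongest reply is that this is a gap in disclosure and not a proven arithmetic error. Getting to 69 requires a 6-month control mean and SD equal to baseline, a two-sided 5% alpha and no separate latent variance, and the plan states none of these. It labels 23.65 (6.85) as baseline values and says other inputs came from sources the reader cannot see. Step 5 shows that a plausible kind of model, with a 23% effect and a control mean of 18, comes near every cell.

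Much of that stands, and it rules out two stronger readings that a reader might infer.

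- *Table 1 was really built on a 10 to 12% effect.* Read as single-visit comparisons at SD 6.85, the six cells do correspond to about 2.35 to 2.83 days. But a single-visit test has no rho, and this reading needs a different effect in each row. The documents do not identify it as the calculation made.
- *The trial is five times larger than it needs to be.* The ratio 346/69 holds only at a control mean of 23.65; at 15 it is 346/168 ≈ 2.1. The documents do not settle which applies.

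What does not stand is that the missing inputs remove the mismatch. The model that comes near Table 1 needs a control mean well below 23.65 and an SD well above 6.85. At 23.65 the same model needs only 65 to 89.

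It is also fair to say that the stated 90% is true as a minimum if the effect is 5.4 days (power at 346 exceeds 99.99%), and that the two-to-three-day range is background and not a declared target. Both limit the consequence. Neither makes the sentence agree with its inputs.

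**Conclusion.** The point holds as a mismatch between the power statement and the only mean and SD the plan gives. With 6-month control values near baseline and a two-sided 5% test, an approximate 23% increase needs about 69 analysed children at 90% power (65 to 89 under the overdispersed-binomial model), against 248 to 346 in Table 1. Reconciling 346 with 23% takes a control mean or an SD that the plan does not state. The models tried are not exhaustive, and the documents do not show which element is at fault.

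The direction is conservative: the trial is not underpowered for 23% at the stated mean and SD, and N=406 is unaffected. A detectable difference of 2.4 days (10%) with 346 analysed is one conditional reading, resting on SD 6.85, two-sided 5% and an unadjusted 6-month comparison. It should be corrected, but it does not threaten the design.

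**What to change.** Keep N=406. Correct the 23% sentence, the SD or the table, whichever the original calculation shows to be wrong, so that these agree: effect in days, 6-month control mean, SD, alpha and sidedness, power model (including the latent-effect variance) and N.

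Then restate the detectable effect as a labelled assumption, for example: *Assuming a 6-month SD of 6.85 and two-sided 5%, 346 analysed children give 90% power for about 2.4 days/month unadjusted (77% power for 2 days), or about 1.7 to 2.1 days with baseline adjustment at rho 0.7 to 0.5.* This should not be presented as the effect on which Table 1 was built.

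The cost is one edited paragraph and, if needed, one table. Enrolment, randomisation and analysis do not change.
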